3.2 Secondary Objectives

[figure not shown]
- Determine if intra-pyloric botulinum toxin injection during a minimally invasive esophagectomy:
 - Reduces the number of repeat procedures for delayed gastric emptying within 90 days,
 - Decreases time to oral intake meeting 100% of nutritional requirements,
 - Reduces the incidence of pulmonary complications directly related to delayed gastric emptying,
 - Reduces hospital length of stay related to delayed gastric emptying and,
 - Increases patient quality of life

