To ensure the radiologist interpreting the nuclear medicine and gastrografin studies/CT esophagram remains blinded, the radiologist should not open the “operative note” documents in

the electronic medical record. During study interpretation, if the radiologist requires clarification regarding the operative procedure, he should contact the operating surgeons directly. The randomization group will not be listed in any other part of the electronic medical record.

Primary Endpoint

- Postoperative delayed gastric emptying assessed radiographically as “severe” by nuclear medicine emptying study compared to “intermediate,” and “rapid” emptying. “Severe” delayed gastric emptying will be defined as scoring of “delayed” on nuclear emptying study. Patients assessed as “intermediate” or “rapid” on nuclear medicine emptying study will be considered to have normal conduit function.

Secondary Endpoints

- Postoperative delayed gastric emptying assessed radiographically by gastrografin swallow /CT esophagram.
- Postoperative delayed gastric emptying assessed clinically by the following:
 1. Quality of life score assessed by EORTC QLQ-C30 OES18.
 2. Pulmonary events directly related to delayed gastric emptying, as assessed by the operating surgeon. Pulmonary events include pneumonia, acute aspiration, and respiratory failure requiring intubation.
 3. Gastrointestinal and nutritional status: Requirement of NGT past Postoperative Day #7, or need to reinsert NGT, witnessed nausea, vomiting, or regurgitation directly related to delayed gastric emptying. This does not include postoperative ileus. Tolerance of full liquid diet at hospital discharge and meeting nutritional goals of time to resumption of 50% caloric needs orally by Postoperative Day #7, 75% caloric needs orally by Postoperative Day #21, and 100% caloric needs orally by Postoperative Day #35.
 - “Moderate” delayed gastric emptying will be defined as clinical symptoms requiring medical therapy.
 - “Severe” delayed gastric emptying will be defined as clinical symptoms requiring secondary procedure.
 4. Hospital length of stay attributed to delayed gastric emptying.
 5. Number of secondary procedures within 90 days due to delayed gastric emptying. Secondary procedures include endoscopic or operative procedures for delayed gastric emptying.
 - Requirement of secondary procedure will be graded as “Severe” delayed gastric emptying

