6.7 End of Study Visit

- At day #90 (\pm 7 days), an end of study phone call will be conducted by the study coordinator. The purpose of this call is to inquire about any subsequent procedures the patient may have undergone related to delayed gastric emptying or esophagectomy, nutrition assessment to determine if the patient continues to require supplemental jejunal feeds, any persistent clinical symptoms of delayed gastric emptying, including any subsequent pneumonia, aspiration events, respiratory failure, nausea, vomiting, ability to eat solid food or drink liquids or having any trouble eating, early satiety, difficulty swallowing saliva, noticing bile or green staining on pillow while sleeping, experiencing acid indigestion or heartburn, or pain with eating, concomitant medications and Clinical Events of Interest and adverse events will be assessed. If the patient indicates continued use of tube feeds, the study coordinator will alert the dietitian to call the patient for further evaluation of the percentage of tube feeds versus oral intake. If the patient is no longer using jejunal feeds, the study coordinator will mark down “100% oral intake.

The schedule of procedures and observations for this study is summarized in **Table 2** below.

Table 2 Schedule of Procedures and Observations

Evaluation	Baseline ¹	Day of Surgery	Inpatient Postoperative Course ² (Surgery to Discharge)	Postoperative Visit #1 ³ ± 14 days	Postoperative Visit#2 ³ ± 14 days	End of Study phone call Day#90 (± 14 days)
Medical History, Pre-Existing Conditions (including smoking status, diabetes)	X					
ECOG Performance Status	X					
Multidisciplinary Evaluation and neoadjuvant therapy for esophageal carcinoma	X					
Physical Examination, including vital signs ⁴	X	X	X	X	X	
Hematology ⁵	X		X		X	
Chemistry ⁶	X		X		X	
Sign study informed consent, if eligible based on above factors	X					
Minimally invasive esophagectomy with or without pyloric drainage procedure		X				
Fasting glucose				X As indicated)		
Chest X-Ray, CT chest			X (As indicated)		X (As indicated)	

Evaluation	Baseline ¹	Day of Surgery	Inpatient Postoperative Course ² (Surgery to Discharge)	Postoperative Visit #1 ³ ± 14 days	Postoperative Visit#2 ³ ± 14 days	End of Study phone call Day#90 (± 14 days)
Gastrograffin swallow evaluation ¹² /CT esophagram			X ^{12a}			
Nuclear Medicine Emptying Study ^{10, 11}				X ¹¹ (Phone call prior to give instructions)		
Clinical Evaluation of Symptoms			X	X ¹¹	X	X

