9 To be recorded from the time of entry into the operating room until the post-operative follow up. Clinical Events of Interest and SAEs will be recorded in the electronic medical record, and found in the patient's operative note, anesthesia records, daily progress notes, consult notes, nutrition notes, and outpatient visit notes.

10 All procedures and evaluations listed are our post-esophagectomy standard of care at RPCI except for Nuclear Medicine Emptying Study, EORTC QLQ OES18 Questionnaire, and routine postoperative assessment by dietician. See Table 1 for definitions, section 4.1. If contraindicated per investigator's discretion, the nuclear medicine emptying study can be extended beyond post-operative Visit #2 at PI's discretion.

11 Evaluation as documented in Appendix C, Nuclear Medicine Questionnaire.

12 CT esophagram or gastrografin swallow.

12^a: As inpatient when clinically indicated.

13 Nutritional goals as defined in Section 6.4: Day tolerating 50% oral feeds, 75% oral feeds, 100% oral feeds.

14 Nutrition assessment will include a 24-hour calorie count on Postoperative Day #6 ±1 day.

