9 STATISTICAL METHODOLOGY

The primary objectives of this study are:

- Determine if intra-pyloric botulinum toxin injection during a minimally invasive esophagectomy decreases postoperative occurrence of delayed gastric emptying, as assessed radiographically by nuclear medicine emptying study.

The secondary objectives of this study are:

- Determine if intra-pyloric botulinum toxin injection during a minimally invasive esophagectomy reduces the number of repeat procedures for delayed gastric emptying within 90 days, decreases time to oral intake meeting 100% of nutritional requirements, reduces the incidence of pulmonary and gastrointestinal complications directly related to delayed gastric emptying, reduces hospital length of stay related to delayed gastric emptying, and increases patient quality of life.

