Secondary Analysis: The secondary outcomes include additional postop procedures, clinically assessed delayed gastric emptying (days to resumption of oral feeding, EORTC QLQ-30 QoL scores, and clinical symptoms of regurgitation, vomiting, and aspiration), delayed gastric emptying assessed by the gastrografin swallow exam/CT esophagram, pulmonary complications (aspiration, respiratory failure requiring reintubation, pneumonia within 3 months of surgery), and hospital length of stay. All variables will be reported by treatment arm using the appropriate descriptive statistics and graphical summaries.

The days to resumption of oral feeding, QoL scores and, hospital length of stay will be compared between treatment arms using the two sided independent-sample, stratified T-test. Normality will be assessed using the Anderson-Darling test and transformations (such as Box-Cox) will be applied, as appropriate. Bootstrap or non-parametric methods will be applied if no normalizing transformations can easily be applied. The rates of moderate clinical delayed gastric emptying (clinical signs of regurgitation, vomiting, and aspiration), moderate delayed gastric emptying (score of 2 or 3 on the gastrografin swallow test/CT esophagram), severe delayed gastric emptying (score of 4 or 5 on the gastrografin swallow test/CT esophagram), and pulmonary complications will be compared between treatment arms using the two-sided CMH exact test.

A previous study demonstrated that the rate of additional postoperative procedures may be lower for patients treated with botulinum (3.9%) as compared to those without botulinum (15.9%). Therefore, the rates of additional postop procedures within 3 months of the original procedure will be compared between treatment arms using a one-sided CMH exact test.

All analyses will be performed in SAS v9 (Cary, NC).

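### The oral-feeding t-test in Section 9.4 has no rule for patients who never reach full oral intake by day 90 or who die first, so as written it compares only those who reached the goal

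*Combined protocol and SAP*

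**What the plan says.** Section 3.2 lists the objective "Decreases time to oral intake meeting 100% of nutritional requirements", and the opening of Section 9 repeats it: "decreases time to oral intake meeting 100% of nutritional requirements". The secondary endpoints in Section 4.1 give three goals, "time to resumption of 50% caloric needs orally by Postoperative Day #7, 75% caloric needs orally by Postoperative Day #21", followed by 100% by day 35. Section 6.4 and Table 2 footnote 13 have the day of each goal recorded: "Nutritional goals as defined in Section 6.4: Day tolerating 50% oral feeds, 75% oral feeds, 100% oral feeds".

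The analysis sentence in Section 9.4 begins: "The days to resumption of oral feeding, QoL scores and, hospital length of stay will be compared between treatment arms using the two sided". The method it goes on to name is a t-test with stratification. Normality is checked by the Anderson-Darling test, then transformations such as Box-Cox are tried. The last resort is: "Bootstrap or non-parametric methods will be applied if no normalizing transformations can easily be applied".

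Follow-up ends at 90 days. The closing phone call in Section 6.7 includes a "nutrition assessment to determine if the patient continues to require supplemental jejunal feeds", and patients still tube-fed are referred to the dietitian. For the others: "If the patient is no longer using jejunal feeds, the study coordinator will mark down" full oral intake. Section 6.6 provides for death and loss to follow-up.

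**The concern.** A t-test needs a number for each patient. A patient still on jejunal feeds at day 90, or one who died before full oral intake, has no day to enter. The fallbacks do not help: a transformation, a bootstrap or a rank test also needs a value, and they are triggered by the shape of the distribution, not by a goal that was never reached.

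Unless a value is assigned, these patients drop out and the arms are compared among reachers only. Membership of that group depends on what happened after randomisation, and the patients removed have the worst outcomes. Those are the outcomes the injection is meant to prevent. The investigators expect no benefit (Sections 1.1 and 1.2), so a null result produced by the omission would be read as support for leaving the injection out. If a rule is chosen only after the data are seen, nobody can show that it was independent of the result.

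**Working it through.** **Text check.** The places where a rule could stand are:
- Section 9.4: a t-test and its fallbacks; no score, censoring or exclusion for patients without a day.
- Section 9.4, intent-to-treat: stated for the primary objective only.
- Section 4.2, replacement: covers patients without the nuclear medicine study. It does not score their oral-feeding time, and it does not reach patients who had the scan but never reached full oral intake.
- Section 6.7: identifies patients still tube-fed at day 90; assigns no analysis value.
- Section 6.6: classifies death and loss; assigns no analysis value.

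The plan states no power or effect size for this endpoint, so there is no figure of its own to reproduce.

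**Inputs.** From the documents: 50 patients, 1:1, three stratification factors (taken as two levels each, 2 × 2 × 2 = 8 cells), two-sided test, 90 days. Assumed: reachers at mean day 35 (the Section 4.1 target day for 100%), SD 8, 5% level, and every share not reaching the goal. The simulations contain no deaths or losses.

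**Expected values at 30% (control) v 10% (Botox) not reaching, same timing among reachers.**
- Reachers: 25 × 0.70 = 17.5 v 25 × 0.90 = 22.5.
- Difference in means among reachers: 35 − 35 = 0 days.
- With non-reachers entered at day 90: control 0.70 × 35 + 0.30 × 90 = 51.5; Botox 0.90 × 35 + 0.10 × 90 = 40.5; difference 11 days.

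The whole effect lies in the patients who are left out.

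**Simulated rejection rates** (3,000 trials per case, stratified tests). Leave-out uses Section 9.4's own sequence: Anderson-Darling, Box-Cox, else a rank test.

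| Not reaching, control v Botox | Botox faster among reachers | Leave-out | Worst-rank Wilcoxon | Log-rank |
|---|---|---|---|---|
| 30% v 10% | 0 days | 5% | 21% | 29% |
| 20% v 5% | 0 days | 5% | 13% | 20% |
| 10% v 4% | 0 days | 5% | 6% | 8% |
| 30% v 10% | 4 days | 31% | 59% | 58% |
| 10% v 5% | 4 days | 35% | 37% | 35% |
| 15% v 10% | 4 days | 35% | 32% | 28% |
| 10% v 10% | 4 days | 35% | 25% | 21% |
| 4% v 4% | 4 days | 38% | 30% | 27% |
| 10% v 10% | 0 days (null) | 5% | 5% | 6% |

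An unstratified version of the first case gives about 5 to 6% for leave-out and about 23% for worst-rank.

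**How often the inclusion rule changes the conclusion.** With the Wilcoxon test held fixed, including or leaving out non-reachers changes whether p < 0.05 in about 6 to 36% of trials across the non-null cases. The high end needs 30% v 10%.

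**Reversal (constructed, not based on any document figure).** Suppose 20% would never reach the goal, and Botox moves three quarters of them to days 60 to 85 (midpoint 72.5).
- Botox reachers: 80% at day 35 and 15% at day 72.5.
- Mean: (0.80 × 35 + 0.15 × 72.5) / 0.95 = 38.875 / 0.95 = 40.9 days, against 35 in control.

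Botox helps these patients, yet its reachers-only mean is 5.9 days worse (simulated 6.0). Section 9.4's sequence is significant against Botox in 19% of trials, the worst-rank test in 2%. With 10% and half moved: (0.90 × 35 + 0.05 × 72.5) / 0.95 = 37.0, so 2.0 days worse; 6% v 2%.

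**The case against.** **The target can be inferred.** This stands. Sections 3.2 and 9 name 100% intake, and no other oral-intake time is an objective. A reader might infer that Section 9.4 tests the 50% goal, because Section 4.1 speaks of resumption next to it. The documents do not support that: in Section 4.1 the word heads one list covering all three goals. What remains is a missing link in 9.4, closed by naming the variable.

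**Data capture is adequate.** This largely stands. The day of each goal is recorded, with dietitian review at the visits. The one gap is that the Section 6.7 call text asks for no day. A reader might infer from Section 6.6 that deaths after day 30 go undated. But death is a serious adverse event under Section 7.2.1, and Section 7.2.2 has new serious events reported to 90 days after the last intervention or until a new treatment starts, so such deaths are largely captured. Section 7.1 lists continued jejunal feeding but does not mention day 90; only Section 6.7 does.

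**Leave-out is not wrong under the null and can have more power.** Both parts stand. It keeps its level at equal shares (5%) and beats worst-rank in three of the eight non-null cases. A reader might infer inflated false positives or a uniform loss of power; neither is shown. The argument is about whom the comparison describes.

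**The size is assumed.** This stands. Comparing leave-out under 9.4's sequence directly with worst-rank also changes the test as well as the inclusion rule, which is why the 6 to 36% above holds the test fixed.

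**One sentence stating any rule would do.** In part. A stated rule would settle pre-specification, but a rule that left non-reachers out would keep the selection.

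**Conclusion.** The gap is real. Section 9.4 applies a t-test to a time that the protocol itself expects some patients not to reach within follow-up, and no section says how to score or censor them or those who die first. As written, the comparison is confined to patients who reached the goal.

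The size in this trial is unknown, because no document gives the share still tube-fed at day 90. If shares differ widely the omission can hide most of the effect, as in the 30% v 10% case; at 10% v 4% it hardly matters; at equal or nearly equal shares it favours leave-out on power. The reversal shows what is possible, not what is likely.

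The correction is worth making before outcomes are compared by arm. It concerns one secondary endpoint; the sample size, primary analysis and stopping rules do not depend on it.

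**What to change.** In Section 9.4:
- Define the variable as days from surgery to 100% oral intake. If the 50% or 75% goal is also to be tested, name it as a separate variable.
- Replace the t-test for this variable with a stratified worst-rank Wilcoxon test in all randomised patients, including those replaced under Section 4.2. Patients still on tube feeds at day 90 rank worse than every patient who reached the goal; deaths before the goal rank worst of all.
- Rank patients lost before the goal as not reaching it, with a sensitivity analysis that censors them at last contact.
- An acceptable alternative is a stratified time-to-event test censored at day 90, with death as a competing event.

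In Section 6.7, add the day full oral intake was reached to the call text, to match Table 2 footnote 13. No new date-of-death field is needed.

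Cost: a few sentences in 9.4 and one line in the call text, standard SAS procedures, no extra visits. The downside is some loss of power when non-attainment is equal or nearly equal across arms (35% to 25% at 10% v 10% with a 4-day shift), plus a little from stratifying 50 patients over 8 cells.

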9.4.1 Adverse Events

The adverse events will be reported by grade using frequencies and relative frequencies. Additionally, the study will be monitored by the RPCI Data and Safety Monitoring Committee, which will assess the progress of the study, the safety data, and critical efficacy endpoints.

9.5 Interim Analysis and Criteria for Early Termination of the Study

An interim analysis will be conducted after $n_1=30$ patients have completed treatment and will consider the following decision rules:

Analysis	Decision Rule
Interim	
1. If $p\text{-value} \leq 0.011396$, then reject H_0 and stop due to superiority.2. If $\hat{\theta} > 1$, then stop due to inferiority.3. Otherwise enroll $n_2=20$ patients

10 ETHICAL AND REGULATORY STANDARDS

10.1 Ethical Principles

This study will not be initiated until the protocol and informed consent document(s) have been reviewed and approved by a properly constituted Institutional Review Board (IRB) or Independent Ethics Committee (IEC). Each participant (or legal guardian) shall read, understand, and sign an instrument of informed consent prior to performance of any study-specific procedure. It is the responsibility of the investigator to ensure that the participant is made aware of the investigational nature of the treatment and that informed consent is given.

The Investigator is responsible for the retention of the participant log and participant records; although personal information may be reviewed by authorized persons, that information will be treated as strictly confidential and will not be made publicly available. The investigator is also responsible for obtaining participant authorization to access medical records and other applicable study specific information according to Health Insurance Portability and Accountability Act regulations (where applicable).

This study will be conducted in compliance with all applicable laws and regulations of the state and/or country and institution where the participant is treated. The clinical trial should be conducted in accordance with the ethical principles embodied in the Belmont Report: Ethical Principles and Guidelines for the Protection of Human Subjects of Research, consistent with good clinical practice and the applicable regulatory requirements and according to the guidelines in this protocol, including attached appendices.

10.2 Informed Consent

The Investigator (or IRB specified designee) is responsible for obtaining written consent from each participant or the participant's legally authorized representative in accordance with GCP guidelines using the approved informed consent form, before any study specific procedures (including screening procedures) are performed. The informed consent form acknowledges all information that must be given to the participant according to applicable GCP guidelines, including the purpose and nature of the study, the expected efficacy and possible side effects of the treatment(s), and specifying that refusal to participate will not influence further options for therapy. Any additional information that is applicable to the study must also be included. Additional national or institutionally mandated requirements for informed consent must also be adhered to. The

participant should also be made aware that by signing the consent form, processing of sensitive clinical trial data and transfer to other countries for further processing is allowed.

The Investigator shall provide a copy of the signed consent form to the participant and the signed original shall be maintained in the Investigator File. A copy of the signed consent form must be filed in the participant file. At any stage, the participant may withdraw from the study and such a decision will not affect any further treatment options.

11 STUDY RESPONSIBILITIES

11.1 Data Collection

Data entry into the REDCap database is to be completed in a timely fashion (within 30 days) after the participant's clinic visit. If an AE is considered serious it is captured on the Serious Adverse Event Source Form, which is handled in an expedited fashion.

Data management activities are performed using a CTMS system that enables the collection, cleaning and viewing of clinical trial data. eCRF data will be collected in REDCap, but Adverse Event data will be collected in Advarra EDC for DSMC reporting.

11.2 Maintenance of Study Documents

Essential documents will be retained per RPCI's policy for 6 years from the study termination date. These documents could be retained for a longer period, however, if required by the applicable local regulatory requirements or by an agreement with RPCI.

12 ADMINISTRATIVE RULES

12.1 Revisions to the Protocol

RPCI may make such changes to the protocol as it deems necessary for safety reasons or as may be required by the U.S. FDA or other regulatory agencies. Revisions will be submitted to the IRB/ERC for written approval before implementation.

12.2 Termination of the Study

It is agreed that, for reasonable cause, either the RPCI Investigators or the Sponsor, may terminate this study, provided a written notice is submitted within the time period provided for in the Clinical Trial Agreement. In addition, RPCI may terminate the study at any time upon immediate notice if it believes termination is necessary for the safety of participants enrolled in the study.

